The Chinese government reported the first cases of pneumonia of unknown origin on December 31, 2019,³ followed by a rapid increase in the Hubei province in China during the first weeks of January 2020, expanding in continental China and neighboring countries. The World Health Organization declared COVID-19 a public health emergency of international concern on January 30, 2020⁴ and a pandemic on March 11, 2020.⁵ The pandemic reached Latin America later than other continents, and the first case of COVID-19 in the region was reported in Brazil on February 26,⁶ followed by a case in Mexico on February 28, 2020 and subsequently spreading throughout the region during March 2020.

Policy responses to COVID-19 in Latin America have sought to reduce viral spread, increase the capacity of the health system response, mitigate negative consequences, and strengthen governance.⁷ Effectiveness studies of social distancing policies in China,^{8,9} India,¹⁰ European countries^{11,12}, the United States¹³ and worldwide¹⁴ have shown that these appear to be effective to reduce viral transmission.

Despite the heavy burden of the COVID-19 in Latin American countries, there have been few studies examining the effectiveness of COVID-19 policies.¹⁵⁻¹⁷ Likewise, few studies have explored variation at the local level in the effectiveness of COVID-19 policies.^{10,13,16} Inequalities in policy effectiveness can arise due to within-country differences at the local level due to their

geographical, sociodemographic, mobility patterns, and governance differences. In Latin America, high levels of poverty, urban density, household crowding, lack of safety nets, unemployment and precarious work cluster geographically and coexist with structural inequities in governance and built environments, thus creating barriers for effective compliance with preventive recommendations and for the implementation of well-functioning contact tracing and isolation mechanisms. Understanding the effectiveness of policies at the local level and exploring potential explanations for effect heterogeneity is essential to reduce the burden of the ongoing COVID-19 pandemic and inform the preparedness for future pandemics.

In this study, we aim, first, to estimate the effectiveness of nonpharmaceutical interventions on SARS-COV2 transmission and COVID-19 mortality in Latin America; second, to examine the effect heterogeneity of transmission and mortality at the local level. Third, assuming we find evidence of moderate to substantial heterogeneity at the local level, we aim to explore potential explanations for this heterogeneity. We will use an interrupted time series method to estimate their effects in each local government, and random effects meta-analysis and meta-regression to obtain pooled effects, heterogeneity estimates and potential explanations.

Methods

Design and setting

The study is a natural experiment where we exploit the variation in the temporal and spatial implementation of policy interventions, aimed to reduce the spread and mortality of COVID-19 in Latin America. The unit of analysis are local governments, i.e. third-tier administrative levels such as municipalities, districts or cantons.

We will include all countries fulfilling the following eligibility criteria: (1) Spanish or Portuguese speaking countries in Latin America, and (2) availability of open data at the subnational level for either of the outcomes. Appendix I presents the eligible countries, the exclusion criteria and the sources of data for each excluded country. To date, eligible countries are Argentina, Brazil, Chile, Colombia, Costa Rica, Guatemala, Mexico, Paraguay, and Peru. These countries represent 80.9%

of the population in Latin America, and the vast majority of SARS-CoV-2 cases and COVID-19 deaths.

Interventions

We will examine the impact of several interventions to tackle the COVID-19 pandemic. These interventions include (i) policies aimed at reducing viral transmission, (ii) policies aimed at increasing the capacity of the health system's response, and (iii) policies aimed at mitigating the negative consequences of the epidemic and potential adverse effects of interventions. We will use the PoliMap taxonomy to categorise the examined policies.¹⁸ Table 1 describes the policy interventions in each policy domain included in the study.

Table 1. Policy interventions included in the study

Domain	Policy interventions
Viral spread (for both outcomes)	Total lockdown Partial lockdown (geographical, step-wise/graduated response) Curfew School closure Closure of shopping malls, gyms, churches, parks Remote work Restrictions to national/subnational mobility Prohibition of mass gatherings
Health systems response (for COVID-19 deaths outcome)	Interventions to increase testing capacity Interventions to increase the number of ICU/critical beds
Mitigation strategies (for both outcomes)	Direct social assistance (in-kind/cash) Cash transfer Withdrawal of pension funds

Comparator

In an interrupted time series analysis, the comparator is a counterfactual outcome defined as the projection of the pre-intervention trend to simulate what would have happened if the policy had not occurred (see Statistical Analysis Plan for definitions).

Outcomes

We will assess three primary outcomes. The first outcome will be the 7-day moving average of daily confirmed cases of COVID-19/SARS-CoV-2. The second outcome is the time-varying reproductive number between the current and previous period.¹⁹ The third outcome is the 7-day moving average of the daily number of deaths by COVID-19 in Latin American subnational regions. For the statistical modelling, these averages will be rounded to the nearest integer. We will consider a 7-day lag as the primary lag. Details on sensitivity analyses can be found in the Statistical Analysis Plan.

We define the outcomes following the official national sources definitions, as each country applies its criteria to define the occurrences and the deaths caused by COVID-19. It is important to note that those criteria are not always clearly stated, but all subnational units are under the same measure at each time.

Data sources

We will obtain COVID-19 cases and deaths data, as well as the covariates, on official government sources, such as the Ministry of Health and Ministry of Science and Technology (see Supplementary Appendix Table S2). The intervention information will come from legal documents, official statements, and quantitative accounts from trustable sources.

Covariates

The first model at the local level does not include covariates (see below). The second model (i.e. the meta-analysis), we will examine the change in heterogeneity after adjusting for several covariates at the local level. Local level covariates include projected population size in 2020, demographic density, age-structure of the population, household density and socioeconomic status. We will use data from official sources of information, primarily the latest national population census in each included country.

Statistical analysis

The Statistical Analysis Plan provides details on the modelling assumptions. We will use an interrupted time series design, where each local government acts as its own control.^{20,21} The main

strength of this design is its capacity to distinguish the effect of the intervention from secular change.²² We will use a Poisson regression to model the count data (for both outcomes) and accounting for overdispersion and secular trends.²³ A full discussion on potential biases and violations of assumptions can be found in the Statistical Analysis Plan.

In a second stage, we will use random effects meta analysis to pool the effect estimates for each intervention or combination of interventions. This analysis informs whether any implemented intervention was effective to reduce COVID-19 cases and deaths and the degree of heterogeneity between the effects at the local level. If we observe high levels of heterogeneity (defined as higher than 50%), we will also use standard meta-regression techniques to assess whether local level determinants (see *Covariates*) can explain the observed heterogeneity.

We will build the models and test the analytical strategy using publicly available data on COVID-19 cases and deaths from Finland and Sweden from January 1 to March 31.

References

2. United Nations Department of Economic and Social Affairs. World Social Report 2020: Inequality in a rapidly changing world. New York, United States: United Nations; 2020.
3. World Health Organization. Report of the WHO-China Joint Mission on Coronavirus Disease 2019 (COVID-19)2020. <https://www.who.int/docs/default-source/coronaviruse/who-china-joint-mission-on-covid-19-final-report.pdf> (accessed March 26, 2020).

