where  $Y_t(1)$  is the sequence of outcomes if we treat the unit at time  $p$  and  $Y_t(0)$  the sequence of outcomes in the absence of treatment. Assumption 1 implies no anticipation of treatment, i.e.  $Y_t(1) = Y_t(0)$  for all  $p \leq t_0$ . In other words,  $\alpha_0 = \theta_0$  and  $\alpha_1 = \theta_1$ . Assumption 2 implies that  $\theta_2$  and  $\theta_3$  are equal to zero.

Violations of assumption 1 include anticipation effects when the subjects of the policy can anticipate its initiation and change their behaviour. In the case of the COVID-19 pandemic, the population might, for example, be more likely to adhere to social distancing recommendations during the discussion of a lockdown or take preventive actions when the incidence of cases increases, even before restrictions such as lockdowns are implemented. Violations of assumption 2 include concurrent changes due to history (other concurrent policy, program or societal changes), selection (changes in the composition of the sample at time  $p$ ), instrumentation (changes in the way the outcome is measured) and mis-specification of the functional form of the time trend (in a classical ITS, time is assumed to be a simple linear term). Violations of assumption 3 can occur due to misspecification of the functional form, including failing to account for a delay of the policy to take effect or failing to account for autocorrelation (which can lead to artificially low standard errors). In an epidemic process, cases over time follow a non-linear trajectory (often an exponential, Gompertz or other complex functional forms). Assuming a linear time trend can lead to incorrect counterfactuals and biased effect estimates.

We will examine and handle potential violations to assumptions in the following way:

Assumption 1. We will assess the existence of anticipation effects by visual exploration and examination of the slope prior to the intervention. If there is evidence of potential anticipation effects, we will use a “quasi-myopic” sensitivity analysis, i.e. an analysis that excludes a period of time where anticipation is expected to have happened from the analyses.

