Assumption 2. We will explicitly incorporate co-occurring interventions in a seven-day period as a combination of interventions. We will also adjust for changes in the case definition of COVID-19 cases and deaths for each of the respective outcomes. We will report in the Supplementary Appendix the exact dates considered in the analysis for each country/subnational unit and the interventions included in each intervention period.

Assumption 3. We will introduce flexible spline functions to account for seasonality and long-term trends. We will add a scale parameter, which will be the Pearson statistic divided by the residual degrees of freedom, to account for potential overdispersion (a violation of the Poisson regression assumption). We will test for autocorrelation using the Durbin-Watson tests and visual plots of the autocorrelation function and partial autocorrelation function. If there is evidence of autocorrelation, we will use the Newey-West method to obtain adjusted standard errors.

Therefore, in the final analysis, we will use Poisson regression to model the count data.. The final model is an extension of the regression described in equation 1 with the specifications described above. The model will include each of the interventions (either as single interventions or combinations of), denoted  $j = 1, \dots, J$ . This method allows estimating simultaneously the effect of several interventions. We will consider interventions implemented within a 7-day period as a combination of interventions, following previous studies. This means that the maximum number of combinations of interventions is 52,  $t = 1, \dots, 52$ . We will estimate the effect of the interventions separately when interventions are separated by at least seven consecutive days and for a maximum period of 30 days. The primary analysis will include a 7-day lag to account for the delay in the intervention to be effective, considering the incubation period of SARS-COV2.

$$(5) \ln(Y_t) = \beta_0 + \beta_{1j}time_{tj} + \beta_{2j}post_{tj} + \beta_{3j}timepost_{tj} + \mu_t$$

This model will be run at the municipal level and, therefore, we expect to run 10,000 regressions multiplied by the number of combinations of interventions at each municipal level. Coefficient  $\beta_{3j}$  is the coefficient of interest and represents the change in slope after the intervention  $j$  at period  $t$ .

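### The Protocol assigns testing-capacity interventions to deaths only and the SAP does not confirm it; if that holds, a testing expansion has no term or label in the primary confirmed-case model

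*Protocol*

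**What the plan says.** Protocol Table 1 has three policy domains. Viral-spread and mitigation policies are marked for both outcomes. The third domain, "Health systems response (for COVID-19 deaths outcome", contains "Interventions to increase testing capacity" and measures to add ICU or critical beds.

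The Protocol's Outcomes section states "We will assess three primary outcomes": confirmed cases, time-varying R, and deaths. Its Statistical analysis section nevertheless refers to two: "We will use a Poisson regression to model the count data (for both outcomes".

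On first-stage adjustment, the Protocol's Covariates section says "The first model at the local level does not include covariates". In the SAP's Analysis methods:

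- The threats to assumption 2 include "instrumentation (changes in the way the outcome is measured".
- The measurement remedy for that assumption is "We will also adjust for changes in the case definition of COVID-19 cases and deaths for each of the respective outcomes".
- Interventions falling within seven days of each other are treated as one combination.
- In the final model, "The model will include each of the interventions (either as single interventions or combinations of". No outcome is singled out.

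The SAP also plans splines for seasonality and long-term trend, placebo tests, and a sensitivity analysis correcting cases and R for under-ascertainment.

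**The concern.** Confirmed cases are a product of infections and testing. Each municipality is its own control over time, so a change in testing during the fitted window is a change in how the outcome is measured. The SAP recognises that kind of threat in general, but its remedy in the primary model covers only changes of case or death definition and co-occurring listed interventions. A testing expansion is not a definition change, and under Table 1 it is not a listed intervention for cases either.

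Two things are at stake. First, one event can carry two labels: lockdown with testing for deaths, lockdown alone for cases. The second stage would then pool different exposures under names that suggest they are comparable. Second, the slope change β3 for cases can absorb a change in ascertainment.

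**Working it through.** **Step 1. The text, side by side.**

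| Question | Protocol | SAP |
|---|---|---|
| Is testing an intervention for deaths? | Yes (Table 1) | Yes, if every intervention enters |
| Is testing an intervention for cases? | No (Table 1) | Not separately stated; no split by outcome |
| Is testing an intervention for R? | Not stated: three outcomes, but labels for deaths or for both | Not stated |
| Are there first-stage covariates? | None | Definition changes adjusted for; testing volume not mentioned |

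**Step 2. Consequence of the seven-day rule if Table 1 governs.** Suppose a lockdown and a testing expansion are enforced three days apart. For deaths, both are listed, so the estimate is a combination. For cases, only the lockdown is listed, so the estimate is pooled with single lockdowns. This follows from the rules alone and needs no simulation.

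**Step 3. Can β3 be affected?** The plan gives no figure to reproduce and the documents contain no testing data, so this is an illustration on assumed values, not the planned analysis.

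Expected daily detections: ln μ(t) = ln 20 + 0.08t − 0.05·max(t, 0) + ln 2·clip((t − s)/14, 0, 1), for t = −30 to 29.

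From the plan: the seven-day average, the seven-day lag, the 30-day maximum period, and a Poisson model with level and slope change. Assumed: growth of 0.08 per day, true β3 of −0.05, detections doubling over 14 days from day s, 30 days before the break, and no noise. Day 0 is the lagged effect date (enforcement + 7), so an expansion starting on the policy's own enforcement date has s = −7.

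Without splines, β3 is −0.0484 when testing does not change; the moving average accounts for the gap from −0.05. With a testing expansion:

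- s = −14: −0.0706, shift −0.0706 + 0.0484 = −0.0222 (effect exaggerated)
- s = −7: −0.0435, shift +0.0049 (almost none)
- s = 0: −0.0248, shift +0.0236 (attenuated)
- s = +10: −0.0174, shift +0.0310 (attenuated)

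**Step 4. With splines.** The SAP gives no knots or degrees of freedom. I added an assumed natural cubic spline with 1 to 4 non-linear columns. Each shift is measured from the same model's fit without a testing change.

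| Non-linear columns | β3, no testing change | Shift, s = −14 | Shift, s = 0 | Shift, s = +10 |
|---|---|---|---|---|
| 0 | −0.0484 | −0.0222 | +0.0236 | +0.0310 |
| 1 | −0.0307 | −0.0173 | +0.1204 | −0.0521 |
| 2 | −0.0377 | −0.0560 | +0.0743 | −0.0163 |
| 3 | −0.0023 | −0.0071 | −0.0363 | −0.0569 |
| 4 | −0.0228 | −0.0450 | +0.0211 | −0.0370 |

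At s = 0 the sign depends on the spline. At s = +10 every spline reverses the sign seen without one. The spline fits also miss −0.05 when testing does not change at all, so their shifts mix the testing effect with a general difficulty in separating a spline from a slope change.

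**Step 5. Would a separate dated testing term help?** Not reliably. Nine scenarios were tried (rise of 1.5, 2 or 3 times; growth of 0.05, 0.08 or 0.15). With splines of 1 to 4 columns and a 10-day gap, the term reduced the error in 8, 6, 9 and 9 of 9. At a 14-day gap with 4 columns it did so in 1 of 9.

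**The case against.** The strongest reply is that there is no conflict. The SAP has no intervention list of its own and refers the reader to the Protocol for background, so its statement about the model can simply mean each intervention that Table 1 assigns to the outcome in question. That is indeed the natural reading. A reader might infer a flat contradiction, but the documents support only an unstated rule. If the SAP sentence were instead meant literally, testing would enter the case model and the gap would close.

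A second reply is that leaving testing out for cases is a sound choice of estimand, because more testing raises confirmed cases mechanically and its coefficient would not be a transmission effect. This stands as a reason not to evaluate testing as a policy for cases. It is not a reason to leave the measurement change unlabelled.

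A third is that ascertainment is already addressed. A reader might infer that the plan ignores it, and that would be wrong: the splines, the placebo tests, the under-ascertainment analysis for cases and R, and a deaths outcome that does include testing are all partial safeguards. None of them changes the label on the primary case estimate or adjusts it for a testing expansion near a policy date. Placebo tests look at dates without a policy, and the under-ascertainment correction is a sensitivity analysis only.

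Finally, nothing in the documents shows that testing expansions clustered near policy dates. That stands in full.

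**Conclusion.** The point holds, conditional on Table 1 governing. The primary case model would then have neither a term nor a label for a testing expansion, and the same event would be pooled under different names for cases and deaths. This is more than a missing detail, because an analyst who follows Table 1 faithfully produces mislabelled and possibly biased case estimates. It should be fixed; my confidence is medium.

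A reader might go on to infer that the case results will be biased by a known amount or in a known direction. The documents do not support that. They give no testing data, the illustration rests on assumed values, a same-day expansion moved β3 by only 0.0049 without splines, and the sign elsewhere changed with timing and spline. The figures show that distortion is possible and should not be quoted as its likely size. Nor do the documents establish that testing is excluded for R: that is only an inference from labels written for two outcomes when there are three. No figure is given for R.

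**What to change.** 1. In Table 1 and the SAP, carry testing-capacity interventions into the confirmed-case and R analyses as an ascertainment event, not as a transmission policy to be evaluated. State which rows of Table 1 apply to R. Leave the ICU-bed measures as they are.
2. Apply the existing seven-day combination rule to testing for cases and R, so that such estimates are labelled and pooled as policy plus testing, not as the policy alone. Do not extend the rule beyond seven days for testing.
3. Add a sensitivity analysis that pools case and R estimates only from windows with no testing expansion in the pre-policy or post-policy days fitted.

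I do not recommend a separate dated testing term as a correction, given its erratic performance once splines are in the model.

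**Cost.** A change to one table row, a few SAP sentences and one extra pooled analysis. Testing dates are already needed for the deaths model. There will be fewer single-policy estimates and some loss of precision, and the restricted analysis may be sparse if expansions were common. Items 2 and 3 label and probe the problem without correcting the primary estimate, and residual bias remains because enforcement dates only approximate testing volume.

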In coefficient of interest at a second stage, we will pool the effects for each intervention -or combination of interventions- (i.e. the coefficient of interest  $\beta_{3j}$  from the local level regression) using a random-effects meta-analysis. This meta-analysis will provide information to obtain a pooled effect estimate and a measure of heterogeneity. We will use the  $I^2$  as a measure of heterogeneity.

If the heterogeneity is moderate or high ( $I^2$  higher than 50%), we will carry out a meta-regression to assess whether subnational level determinants can explain the observed heterogeneity. We will analyse the following covariates: (i) Population size, (ii) Population density, (iii) Proportion of population over 60 years old, as a proxy for age structure of the population, (iv) Household density, and (iv) Proportion of population with basic education, as a proxy of socioeconomic status.

The meta-regression has the effect size  $\widehat{\theta}_k$  of a first-stage regression  $k$  as the outcome, covariates  $x_{ik}$ , a fixed effect  $\rho_1 S_a$  for the second-tier level  $a$  (i.e. State or Region) and a random-effect  $\delta_2 N_b$  for the national level  $b$  and a fixed effect  $\rho_2 Y$  for the time of the year (quarterly periods)(equation 6). The equation includes two types of independent errors, where  $\varepsilon_k$  is the sampling error of the effect size and  $\varsigma_k$  is the random-effect error term.

$$(6) \theta_k = \gamma_1 x_{1k} + \dots + \gamma_n x_{nk} + \rho_1 S_a + \delta_2 N_b + \rho_2 Y + \varepsilon_k + \varsigma_k$$

These controls for higher levels of administration and time of the year will allow us to control for constant characteristics at the subnational and national level, as well as changes in the effectiveness throughout the pandemic.

We will carry out the following sensitivity analyses: (1) comparison of effect estimates using a 5-day and 10-day lag; (2) quasi-myopic analyses to control for anticipatory effects (if there is evidence of), and (3) placebo tests evaluating changes at times when no policy was implemented. In the analyses for the number of cases and time-varying R, we will run additional sensitivity analyses estimating the number of SARS-CoV-2 cases corrected by under-ascertainment derived from mortality statistics.

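### Testing-capacity policies are judged only on officially counted deaths; where counting depends on a test, beta3 mixes effect with ascertainment, in either direction, and no planned check covers deaths

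*Protocol*

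**What the plan says.** Protocol Table 1 lists "Interventions to increase testing capacity" in the domain labelled "Health systems response (for COVID-19 deaths outcome". The other two domains are marked for both outcomes, so deaths are the only endpoint on which testing is judged.

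Under Outcomes, the protocol states: "The third outcome is the 7-day moving average of the daily number of deaths by COVID-19 in Latin American subnational regions". On how a death is counted, it says that "each country applies its criteria to define the occurrences and the deaths caused by COVID-19", and it adds that "those criteria are not always clearly stated, but all subnational units are under the same measure at each time".

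The first-stage model (SAP, Analysis methods, equation 5) is a log-linear Poisson regression with a level change beta2 and a slope change beta3. It uses a 7-day lag and an effect period of at most 30 days. Beta3 is the coefficient of interest and is pooled by random-effects meta-analysis. The protocol's Statistical analysis section says of that pooling: "This analysis informs whether any implemented intervention was effective to reduce COVID-19 cases and deaths".

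The SAP lists instrumentation, meaning a change in how the outcome is measured, among the violations of Assumption 2. Its remedy is to adjust for changes in the case definition of cases and deaths. It also plans a correction for under-ascertainment: "In the analyses for the number of cases and time-varying R, we will run additional sensitivity analyses estimating the number of SARS-CoV-2 cases corrected". That correction takes mortality statistics as its reference.

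**The concern.** An interrupted time series needs the outcome to be measured in the same way before and after the policy. A testing-capacity policy can break this condition by its own action. If a death enters the official count only with a test, or more readily with one, wider testing changes the fraction of COVID-19 deaths that is counted while the written definition stays the same. Beta3 then reflects both the change in deaths and the change in counting, and the model cannot separate them.

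At stake is the conclusion on testing, and on any 7-day combination that includes testing. The pooled beta3 would be read as effectiveness when its sign may come from ascertainment. Pooling does not average out a distortion that the policy itself produces. Local differences in that distortion would also add to I² and could be credited to covariates in the meta-regression.

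**Working it through.** The plan states no figure on this point, so there is nothing to reproduce. The check has two parts: whether any planned analysis covers the problem, and how large the bias could be under stated assumptions.

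**1. Coverage by the planned safeguards (SAP, Analysis methods)**

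- Adjustment for definition changes: does not apply when testing expands under an unchanged definition.
- Under-ascertainment analysis: cases and R only. It relies on mortality statistics, which are the series in doubt here.
- 5-day and 10-day lags, and the quasi-myopic analysis: these address timing.
- Placebo tests: run at times when no policy was implemented, so they cannot show a distortion that the policy causes.
- The protocol's assurance that all subnational units are under the same measure at each time concerns comparison between units. Each unit is its own control, so the threat is change over time within a unit.

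None of these covers death ascertainment.

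**2. Illustrative size**

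From the SAP: log link, beta3 as a daily slope, 30-day maximum, 7-day lag, 7-day average. Assumed, because the documents give no values: the counting ratio r (share of deaths counted after the policy divided by share before), the true effect, and the speed at which counting rises.

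Counted deaths = true deaths × share counted. If both change steadily over 30 days:

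apparent beta3 = [ln(true death ratio) + ln(r)] / 30

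With no true effect:

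- r = 1.2: ln(1.2)/30 = +0.006 per day
- r = 1.4: ln(1.4)/30 = +0.011 per day
- r = 2.0: ln(2.0)/30 = +0.023 per day

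With a true 20% fall over 30 days, ln(0.8)/30 = -0.0074:

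- r = 1.10: (-0.2231 + 0.0953)/30 = -0.0043
- r = 1.25: 0.0000
- r = 1.40: +0.0038
- r = 2.0: +0.0157

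The sign reverses once r exceeds 1/(true death ratio): 1.11 for a 10% fall, 1.25 for 20%, 1.43 for 30%.

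The closed form assumes a gradual rise. To vary the speed, equation 5 was fitted without noise: flat baseline, 40 pre-policy days, 7-day trailing average, 7-day lag, 30 days after the lag, no splines, no rounding, no true effect. The bias in beta3 per day was:

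| Rise in counting | r = 1.2 | r = 1.4 | r = 2.0 |
|---|---|---|---|
| Over 30 days | +0.006 | +0.010 | +0.021 |
| Over 7 days | +0.001 | +0.001 | +0.002 |
| One step on the policy date | -0.002 | -0.004 | -0.009 |

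The step result has a simple cause. Most of the jump goes into beta2. The 7 lag days are fitted as pre-policy, so the rise within them tilts beta1 upward. The later series is flat, so beta3 must be negative to offset beta1. The size depends on how the pre-policy days are laid out: a comparable fit with about 40 such days gave -0.0048 at r = 1.4 (with beta2 about +0.20) and -0.0115 at r = 2.0. In that same fit, a true 20% fall gave beta3 = -0.0071 with unchanged counting and -0.0119 with a step of r = 1.4, so the benefit was exaggerated.

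**The case against.** The strongest objection is that the mechanism is conditional and its direction is open. Neither document says that any of the nine countries requires a positive test to count a death. Where deaths without a test are counted, the bias is smaller. That stands.

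A reader might infer that more testing raises counted deaths as a matter of course, so that a useful policy will look harmful. The documents do not support this. The test requirement is unknown, and beta3 is a slope with a separate level term, so a fast rise in counting can leave it almost unbiased or push it toward apparent benefit.

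The counting ratios, true effects and rollout shapes are all assumed, and the calculations omit the splines that the SAP plans. That also stands, and the figures show possible size only.

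The plan deserves some credit. It names instrumentation, and Table 1 keeps testing policies away from case counts, where dependence on testing is most direct. This lessens the problem but does not remove it, because the stated remedy stops at changes in definition.

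Finally, dropping the testing estimate before any death definition has been checked would be out of proportion, and a series of confirmed plus suspected deaths is not free of testing effects either, since a negative test may remove a suspected death. Both points are accepted and shape the fix.

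**Conclusion.** The concern holds in conditional form. Testing-capacity policies are judged on one endpoint, the policy can alter how that endpoint is counted, and no planned adjustment or sensitivity analysis covers deaths. Where counting depends on a test, neither the sign nor the size of beta3 for testing can be read as effectiveness.

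If counting rises by a factor of 1.2 to 2.0, the illustrative bias runs from about -0.009 per day (one step, largest ratio) to +0.023 per day (steady over 30 days, largest ratio), and is near zero for a rise completed in 7 days. These values rest on the assumed ratios, a flat baseline and a model without splines. The documents cannot show which case applies in which country.

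The point is limited to one of the 13 policy types in Table 1 and the combinations that include it. It does not undermine the study as a whole.

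**What to change.** 1. In the SAP's list of sensitivity analyses, add one for deaths under testing policies: refit the model on confirmed plus suspected or probable deaths wherever the national file carries them. State that this series may itself depend partly on testing.
2. List, by country, whether a counted death requires a test, and pool testing-policy estimates separately on that basis. Since the criteria are not always clearly stated, allow a group for countries where this cannot be established.
3. Report beta2 beside beta3 for testing and for every 7-day combination that includes testing.
4. In countries that count test-confirmed deaths only, keep testing in the model and report its estimate, but do not interpret it, or that of a combination containing it, as evidence of effectiveness or harm. A footnote to Protocol Table 1 should say so.

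The cost is wording in two documents, a check of nine national definitions, and one extra model run where the field exists; the documents do not show that any file has it. The downside is a weaker conclusion for testing and for the combinations that include it.
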